4.1.1 Primary Safety Endpoints

The primary safety endpoints include the following:

- 1. Incidence of adverse events through Day 365.
- 2. Change from Baseline in clinical chemistry, hematology, u/a at Days 15, 28, 59, 91, 180 and 365.
- 3. Injection site reactions, as measured by assessments at Days 1, 8, 15, 21, 28, and 59 using National Cancer Institute's Common Terminology for Adverse Events v3.0 criteria as follows:

Grade 1=Pain, itching, erythema;

Grade 2=Pain or swelling with inflammation or phlebitis;

Grade 3=Ulceration or necrosis that is severe or operative intervention indicated.

4. Clinically significant changes in physical examination from Baseline at Days 15, 28, 59, 91, 180 and 365.

Secondary Efficacy Endpoints

The Secondary Efficacy endpoints include the following:

- 1. Change from Baseline in hemodynamic measurements (Appendix B: ABI, TBI, and Wave Form Analysis) and TcPO₂ at Days 15, 28, 59, 91, 180 and 365.
- 2. Change from Baseline in subject-assessed pain, as measured by the VAS (Appendix C) at Days 15, 28, 59, 91, 180 and 365.
- 3. Change from Baseline in ulcer area, in square millimeters, as assessed by digital photograph and measurement of the largest contiguous ulcerated area, at Days 15, 28, 59, 91, 180 and 365.

Pharmacokinetic Evaluations

Pharmacokinetics of VM202 will be assessed using blood VM202 DNA concentration levels from samples obtained pre-dose at the first dose administration (Day 1). In addition, levels will be measured at Days 21, and 59 (if DNA is detected at Day 21).

Pharmacodynamic Evaluations

Pharmacodynamics will be assessed as the change from Day 1 in serum HGF level at Days 8, 15, 21 and 59. Potential immune response to HGF will be assessed as change

from Day 1 in level of neutralizing antibodies (anti-HGF antibodies) at Days 15, 28, 59 and 180. The ability of HGF to stimulate cell growth will be assessed as the change from Baseline in level of endothelial progenitor cell assay at Days 15, 28, 59 and 180.

Overall Study Design

The overall trial design includes: 1) a multi-dose Phase I safety and tolerability evaluation; 2) a preliminary efficacy, pharmacokinetic and pharmacodynamic evaluation; and 3) a safety review between dosing cohorts in order to meet defined safety criteria. The study will evaluate vascular assessments as primary measures of efficacy and adverse event collection and laboratory parameters as the primary monitored measures of safety (see Table 4-1).

Study Population

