7.1.6 Local Injection Site Reaction Assessment

Local injection sites reactions will be assessed using the grading defined by the National Cancer Institute's Common Terminology for Adverse Events v3.0. The grading categories are as follows and will be recorded on the CRF:

Adverse Event	Grade 1	Grade 2	Grade 3	Grade 4	Grade 5
Injection site reaction	Pain; itching; erythema	Pain or swelling, with inflammation or phlebitis	Ulceration or necrosis that is severe; operative intervention indicated		
Ulceration		Superficial ulceration <2 cm size; local wound care; medical intervention indicated	Ulceration ≥2 cm size; operative debridement, primary closure or other invasive intervention indicated (e.g. hyperbaric oxygen)	Life- threatening consequences; major invasive intervention indicated (e.g., complete resection, tissue reconstruction, flap, or grafting	Death
Allergic reaction/ hypersensitivity	Transient flushing or rash; drug fever <38°C (<100.4°F)	Rash; flushing; urticaria; dyspnea; drug fever ≥38°C (≥100.4°F	Symptomatic bronchospasm, with or without urticaria; parenteral medications(s) indicated; allergy-related edema/ angioedema; hypotension	Anaphylaxis	Death

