8.0 Adverse Events and Serious Adverse Events

8.1 Adverse Event Definition

An AE is the development of an undesirable medical condition or the deterioration of a pre-existing medical condition following or during exposure to a pharmaceutical product, whether or not considered causally related to the product. AEs will be graded according to the National Cancer Institute's Common Terminology for Adverse Events v3.0 criteria.

An undesirable medical condition can be symptoms (e.g., nausea, chest pain), signs (e.g., tachycardia, enlarged liver) or abnormal results of an investigation (e.g., laboratory findings, electrocardiogram).

Therefore, an AE would include the following:

- Any event that is new (i.e., was not seen prior to the start of the study).
- A condition detected or diagnosed after the trial medication administration, even though it may have been present prior to the start of the study.
- A pre-existing intermittent event or condition that recurs with increased intensity and/or frequency after the start of the study.
- A pre- or post-treatment event that results from study participation (i.e., invasive procedures, modification of subject's therapeutic regimen)
- A change in blood pressure or heart rate that results in discontinuation of dosage or that exceeds protocol-specified criteria

An AE does not include the following:

- The disease or disorder being studied, or a sign or symptom of that disease or disorder, unless it is more severe than expected for the subject's condition.
- An overdose of the study medication if the subject is asymptomatic.
- A medical or surgical procedure (e.g., surgery, endoscopy, tooth extraction).
 Depending on the trial design, such a procedure may be the result of an AE or may result in an AE, but is not an AE itself.
- A pre-existing condition or disease that does not worsen following study drug administration.
- Hospitalization for elective surgery for a pre-existing disease or condition that did not worsen or for cosmetic surgery.

In this study an AE can include an undesirable medical condition occurring at any time after screening procedures have been started until the final follow-up visit, even if no study treatment has been administered.

When an adverse event occurs, the Investigator must:

- 1. assess whether or not the test article caused the AE;
- 2. determine the intensity of the AE;
- 3. record the action taken regarding the test article;

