- 4. indicate whether the AE led to discontinuation of the subject from the study; and
- 5. determine if the AE is serious.

All AEs that occur in any subject enrolled, before treatment, during treatment, or up to and including study Day 365 whether or not related to the study drug, must be recorded on the appropriate CRF form provided.

The following are definitions of levels of severity:

- Mild: an awareness of symptoms but easily tolerated
- Moderate: symptoms interfering with daily activities
- Severe: incapacitating, with inability to perform normal daily activities.

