10.9 Injection Site Reaction

Assessments of the existence of an injection site reaction are planned for Day 1 (Post-Dose), Day 8, Day 15 (Post-Dose), Day 16, Day 21, Day 28 and Day 59. The number and percentage of subjects with an injection site reaction will be summarized.

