| | Results/ Pregnancy Outcome | |
| 7 | Ulcer Measurements | 16 |
| 8 | High Resolution MRA/ Injection Site Reaction | 16 |
| 9 | Assessment of CLI | 17 |
| 10 | Hemodynamic Assessments | 18 |
| 11 | Visual Analogue Scale for Pain | 19 |
| 12 | Transcutaneous Oxygen Pressure Assessment- TcPO ₂ | 19 |
| 13 | Concomitant Medications Identified as being Analgesic in | 98 |
| | Nature | |
| 14 | Study Drug Administration | 20 |
| 15 | Adverse Events | 97 |
| 16 | Serious Adverse Events | 97 |
| 17 | Hematology | 11 |
| 18 | Chemistry | 12 |
| 19 | Urinalysis | 13 |
| 20 | Physical Examinations | 7,8 |
| 21 | Vital Signs | 9 |
| 22 | Retinal Fundoscopy/ Chest X-Ray/ CT Scan | 10 |
| 23 | Infection Tests | 14 |
| 24 | Tumor Markers | 15 |
| 25 | Concomitant Medications | 98 |
| 26 | VM202 DNA Levels (include Collection Date/Time from CRF) | 16, Lab |
| 27 | Endothelial Progenitor Cell Assay | 14 |
| 28 | Serum HGF/ Anti HGF Antibodies (include Collection | 14, Lab |
| | Date/Time from CRF) | |
| 29 | Telephone Follow-Up Contact | 22 |
| 30 | Waiver | 23 |

List of Data Listings (cont)

| Listing | | CRF |
|---------|---------------------|----------|
| Number | Listing Description | Plate(s) |
| 31 | Death | 101 |

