| | Number of | Number of | Number of | Number of | Number of | Number of | Number of | Number of |
| System Organ Class / Preferred Term | Subjects [1] | Events | Subjects [1] | Events | Subjects [1] | Events | Subjects [1] | Events |
| Subjects Reporting at Least One Adverse Event | n (%) | n | n (%) | n | n (%) | n | n (%) | n |
| System Organ Class 1 | n (%) | n | n (%) | n | n (%) | n | n (%) | n |
| Preferred Term 1 | n (%) | n | n (%) | n | n (%) | n | n (%) | n |
| Preferred Term 2 | n (%) | n | n (%) | n | n (%) | n | n (%) | n |
| | | | | | | | | |
| • | | | | | | | | |
| System Organ Class 2 | n (%) | n | n (%) | n | n (%) | n | n (%) | n |
| Preferred Term 1 | n (%) | n | n (%) | n | n (%) | n | n (%) | n |
| Preferred Term 2 | n (%) | n | n (%) | n | n (%) | n | n (%) | n |

[1] At each level of summation (overall, system organ class, preferred term), subjects reporting more than one adverse event are counted only once.

Protocol Number: US-06-1-001

Table 13
Treatment Emergent Adverse Events by System Organ Class and Severity [1]
Safety Population
Part 1 of 2

| | VM202-2 mg (N=) | | | | | VM202-4 mg (N=) | | | | |
|--|-------------------------|-------------------------|-------------------------|-------------------------|-------------------------|-------------------------|-------------------------|-------------------------|-------------------------|-------------------------|
| System Organ Class / Preferred Term | Mild | Moderate | Severe | Life Threat. | Death | Mild | Moderate | Severe | Life Threat. | Death |
| Subjects Reporting at Least One Adverse Event | n (%) |
| System Organ Class 1 | n (%) |
| Preferred Term 1 | n (%) |
| Preferred Term 2 | n (%) |
| | | | | | | | | | | |
| - | | | | | | | | | | |
| System Organ Class 2 Preferred Term 1 Preferred Term 2 | n (%) n (%) n (%) |

^[1] At each level of summation (overall, system organ class, preferred term), subjects reporting more than one adverse event are counted only once using the highest severity.

Protocol Number: US-06-1-001

Table 13
Treatment Emergent Adverse Events by System Organ Class and Severity [1]
Safety Population
Part 2 of 2

| | VM202-8 mg (N=) | | | | | VM202-16 mg (N=) | | | | | |
|---|------------------|----------|--------|--------------|-------|-------------------|----------|--------|--------------|-------|--|
| System Organ Class / Preferred Term | Mild | Moderate | Severe | Life Threat. | Death | Mild | Moderate | Severe | Life Threat. | Death | |

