| Subject reported an Injection Site I | Reaction? | | | |
| Yes | n (%) | n (%) | n (%) | n (%) |
| No | n (%) | n (%) | n (%) | n (%) |

path\t_program.sas date time

Programmer Note:

Viromed Co., Ltd. Protocol Number: US-06-1-001

Table 24 Concomitant Medications [1] Safety Population

| ATC Drug Class / Medication Term | VM202- 2 mg | VM202- 4 mg | VM202- 8 mg | VM202- 16 mg |
|--|-------------|-------------|-------------|--------------|
| | (N=) | (N=) | (N=) | (N=) |
| Subjects Receiving any Concomitant Medications | n (%) | n (%) | n (%) | n (%) |
| Drug Class 1 Medication Term 1 Medication Term 2 | n (%) | n (%) | n (%) | n (%) |
| | n (%) | n (%) | n (%) | n (%) |
| | n (%) | n (%) | n (%) | n (%) |
| Drug Class 2 | n (%) | n (%) | n (%) | n (%) |
| Medication Term 1 | n (%) | n (%) | n (%) | n (%) |
| Medication Term 2 | n (%) | n (%) | n (%) | n (%) |

[1] At each level of summation (overall, ATC drug class, medication term), subjects reporting more than medication are counted only once.

path\t_program.sas date time

Viromed Co., Ltd. Protocol Number: US-06-1-001

Table 25 VM202 DNA Levels (unit) ITT Population

| | VM202- 2 mg (N=) | | VM202-4 mg (N=) | | VM202-8 mg (N=) | | VM202-16 | i mg (N=) |
|--------------|-------------------|--------------|------------------|--------------|------------------|--------------|--------------|--------------|
| | Result | Change [2] | Result | Change [2] | Result | Change [2] | Result | Change [2] |
| Baseline [1] | | | | | | | | |
| N | n | | n | | n | | n | |
| Mean (SD) | xx.x (xx.xx) | | xx.x (xx.xx) | | xx.x (xx.xx) | | xx.x (xx.xx) | |
| Median | XX.X | | XX.X | | XX.X | | XX.X | |
| Min, Max | XX, XX | | XX, XX | | XX, XX | | XX, XX | |
| Day 21 | | | | | | | | |
| N | n | n | n | n | n | n | n | n |
| Mean (SD) | xx.x (xx.xx) | xx.x (xx.xx) | xx.x (xx.xx) | xx.x (xx.xx) | xx.x (xx.xx) | xx.x (xx.xx) | xx.x (xx.xx) | xx.x (xx.xx) |
| Median | XX.X | XX.X | XX.X | XX.X | XX.X | XX.X | XX.X | XX.X |
| Min, Max | XX, XX | XX, XX | XX, XX | XX, XX | XX, XX | XX, XX | XX, XX | XX, XX |
| Day 59 | | | | | | | | |
| N | n | n | n | n | n | n | n | n |
| Mean (SD) | xx.x (xx.xx) | xx.x (xx.xx) | xx.x (xx.xx) | xx.x (xx.xx) | xx.x (xx.xx) | xx.x (xx.xx) | xx.x (xx.xx) | xx.x (xx.xx) |
| Median | XX.X | XX.X | XX.X | XX.X | XX.X | XX.X | XX.X | XX.X |
| Min, Max | xx, xx | xx, xx | xx, xx | xx, xx | xx, xx | xx, xx | xx, xx | xx, xx |

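### Primary safety endpoint 3 is a graded injection site reaction at named days, but SAP 10.9 and Table 23 report only whether a subject had any reaction, so no dedicated by-cohort summary shows local grade or timing.

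*SAP*

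**What the plan says.** Protocol 4.1.1 lists four primary safety endpoints. The third is "Injection site reactions, as measured by assessments at Days 1, 8, 15, 21, 28, and 59", measured with CTCAE v3.0 and set out as Grades 1, 2 and 3. Protocol 7.1.6 repeats the scale in a table and says of it: "The grading categories are as follows and will be recorded on the CRF".

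SAP 10.9 names seven assessments: Day 1 post-dose, Day 8, Day 15 post-dose, and Days 16, 21, 28 and 59. Day 16 is not in Protocol 4.1.1 but is in Protocol Table 4-1. SAP 10.9 describes these as assessments of whether a reaction exists, and its only planned summary is: "The number and percentage of subjects with an injection site reaction will be summarized".

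The Table 23 shell in SAP Appendix B turns this into one question, beginning "Subject reported an Injection Site", with a Yes row and a No row for each of the four dose cohorts. It has no grade rows and no visit rows, and its programmer note is blank.

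Elsewhere in the SAP, injection site reaction appears by name in Listing 8, titled "High Resolution MRA/ Injection Site Reaction". The listing's columns are not shown.

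**The concern.** The primary objective is safety and tolerability, and the product is injected locally. Local tolerability by dose is therefore one of the main things the final report should describe. Protocol 6.1.1 sets up a clear local gradient: from Cohort II to Cohort IV the number of injections per administration stays at 8 while the dose and volume at each site rise. Two descriptive questions follow. Does local grade rise along that gradient, and does it change when the same leg is injected again at Day 15?

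Table 23 can answer neither. The SAP states a specific rule, and following it as written collapses the grade and timing of a primary endpoint to Yes or No. This is not a detail left open for later.

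**Working it through.** No sample size, power or alpha figure is involved, and the plan gives no number to reproduce. The check sets the definitions beside the outputs and counts what each output can show.

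**1. Endpoint against summary**

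| | Protocol 4.1.1 and 7.1.6 | SAP 10.9 and Table 23 |
|---|---|---|
| Variable | Grade 1, 2 or 3, or none | Reaction, yes or no |
| Time | 6 named days | 7 assessments collected, none shown separately |
| Cells per cohort | 6 x 4 = 24 (7 x 4 = 28 with Day 16) | 2 |

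The sentence in SAP 10.9 could by itself be read as a summary at each visit. The shell settles it. Table 23 has no time rows and no instruction to repeat, whereas the shells for Tables 5, 8 and 25 to 27 carry an explicit note to repeat for all time points, and SAP 10.7 says by visit for infection tests.

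**2. The other three primary safety endpoints**

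- Adverse events: by highest severity (SAP 10.2, Table 13), not by visit.
- Laboratory values: at each time point (SAP 10.3), with a shift to the most abnormal result.
- Physical examination: shift at each follow-up visit (SAP 10.4).

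There is no uniform layout, but each keeps either severity or time. Only injection site reaction loses both.

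**3. What the Yes cell hides**

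Give each subject a worst grade (0 to 3) after the first administration and another after the second. There are 4 x 4 = 16 possible pairs. One pair, (0,0), prints as No. The other 15 print as Yes: grade higher after the second administration in 6, lower in 6, equal and non-zero in 3. These are counts of what the table can distinguish, not probabilities.

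**4. The dose gradient (Protocol 6.1.1)**

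| Cohort | Dose per site | Volume per site | Injections per administration |
|---|---|---|---|
| I | 0.25 mg | 0.5 ml | 4 |
| II | 0.25 mg | 0.5 ml | 8 |
| III | 0.5 mg | 1.0 ml | 8 |
| IV | 1.0 mg | 2.0 ml | 8 |

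Dose per site from II to IV: 1.0 / 0.25 = 4-fold, with the number of injections constant. From I to II the dose per site does not change and the number of injections doubles.

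**5. A trap for any comparison of the two administrations**

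SAP 10.9 has 2 assessments after the first dose (Day 1 post-dose, Day 8) and 5 after the second (Day 15 post-dose, Days 16, 21, 28, 59). The chance of at least one reaction in k looks is 1 - (1 - p)^k. The documents give no p, so assume independent looks with the same p at each:

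| p per look | 2 looks | 5 looks |
|---|---|---|
| 5% | 10% | 23% |
| 10% | 19% | 41% |
| 20% | 36% | 67% |

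A plain worst grade after dose 1 against worst grade after dose 2 would thus tend to look worse after dose 2 with no true difference. Matched windows avoid this: Day 1 post-dose and Day 8 (0 and 7 days after the first dose) against Day 15 post-dose and Day 21 (0 and 21 - 15 = 6 days after the second).

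**The case against.** The strongest reply is that the information is not lost.

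- **Listings.** SAP section 4 commits individual CRF data to by-subject listings, Protocol 7.1.6 puts the grade on the CRF, and Listing 8 names injection site reaction. Read together, these point to the grade being listed. This stands. With 3 subjects in a cohort, or 6 after a dose-limiting toxicity, a listing is a workable source. It is still not a by-cohort summary, and its columns are not specified.
- **Adverse event tables.** A new reaction after dosing fits the adverse event definition in Protocol 8.1, which says "AEs will be graded according to the National Cancer Institute's Common Terminology for Adverse Events v3.0 criteria". Table 13 would then show it by cohort and worst severity under "Mild | Moderate | Severe | Life Threat. | Death". This stands in part. The SAP does not say that injection-site assessments feed the adverse event tables, Table 13 has no visit dimension, and Protocol 8.1 also gives a second scale ("Mild: an awareness of symptoms but easily tolerated"), so a Table 13 column need not equal the 7.1.6 grade.
- **No promised table.** Protocol 9.3 specifies no injection-site summary, so the SAP breaks no stated analysis. True, but the endpoint definition sets what is measured, and a Yes/No result does not report it.
- **Small numbers.** One subject of 3 is 33 percentage points, so no dose trend can be established. True, and no test is proposed. The SAP already tabulates many variables by visit at this cohort size.

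A reader might infer that the grade goes unreported, or that escalation decisions are made blind to local severity. The documents support neither. The listing commitment answers the first. On the second, Protocol 9.4 has the safety committee review severity before each next cohort is dosed, and Protocol 7.1.9 makes injection-site necrosis within two weeks a dose-limiting toxicity.

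**Conclusion.** The mismatch is confirmed, and its scope is narrow. A primary safety endpoint defined by grade and day is planned as a single Yes/No per subject: 2 cells per cohort where the definition has 24, or 28 with Day 16. The loss is confined to the dedicated by-cohort summary of local grade and its timing in the final report. Subject protection and dose escalation are not affected.

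This rests on the SAP text and shells being followed as written. It also assumes that Listing 8 will show grade, which SAP section 4 implies but the listing index does not confirm. If Listing 8 carries only Yes/No, the loss is larger. If every reaction is also entered as an adverse event on the CTCAE scale, worst grade by cohort is recoverable from Table 13 and only timing is missing. The point should be corrected before the tables are produced. It is a reporting defect, not a flaw in the design.

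**What to change.** Revise SAP 10.9 and Table 23 as follows.

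1. Show, by cohort, the number and percentage of subjects at each 7.1.6 injection-site grade (0 to 3) at each scheduled assessment: Day 1 post-dose, Day 8, Day 15 post-dose, and Days 16, 21, 28 and 59.
2. Add each subject's worst grade overall.
3. If the two administrations are compared, use the matched windows (Day 1 post-dose and Day 8 against Day 15 post-dose and Day 21), take the subjects given that administration as the denominator, and flag reactions still ongoing from the first.
4. State that Listing 8 shows grade and assessment day.

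The cost is one revised shell and a few sentences, with no new visit, test or subject. The table grows from 2 rows to 7 x 4 + 4 = 32 rows per cohort, before any matched-window rows. It will be sparse with about 3 subjects per cohort and should be read as description only. The CRF pages are not in the documents, so first confirm that grade is held as a coded field.

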10.10 Prior and Concomitant Medications

Verbatim terms on case report forms will be mapped to Anatomical/Therapeutic/Chemical (ATC) Level 4 categories and Drug Reference Names using the World Heath Organization (WHO) dictionary (version 5.3).

Prior medications are those medications taken within 30 days prior to the initial dose of study drug. Concomitant medications are those medications taken after the initial dose of study drug. Prior and concomitant medications will be summarized for each treatment by

WHO ATC class and medication name. These summaries will present the number and percentage of subjects using each medication. Subjects may have more than one medication per ATC category and medication. At each level of subject summarization, a subject is counted once if he/she reported one or more medications at that level. Each summary will be ordered by descending order of incidence of ATC class and medication within each ATC class.

11. PHARMACOKINETICS

VM202 DNA levels will be determined before dose on Day 1. In addition, VM202 DNA levels will be collected on Day 21 and Day 59 (if DNA is detected on Day 21). VM202 DNA level results will be summarized using descriptive statistics at baseline and at each post baseline time point. Changes from baseline will also be summarized.

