3.2 Secondary Objectives

The secondary objectives of the study will include the following exploratory evaluations:

- To investigate the effects of the intramuscular VM202 to improve pain at rest and/or to heal ischemic ulcers of the affected limb. The VAS assessment tool will be used for this evaluation.
- To evaluate the anatomic and physiological extent of collateral vessel development in subjects with critical limb ischemia as measured by MRA.
- To evaluate the change in serum HGF levels from Day 1 to Day 59.
- To evaluate the change in VM202 DNA levels from Day 1 to Day 21.
- To evaluate the immune response to HGF in subjects with CLI as measured by the change in anti-HGF antibodies from Day 1.
- To evaluate the ability of VM202 to stimulate endothelial progenitor cells as measured by the change in endothelial cell progenitor assay levels from screening to Day 59.

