Tumor markers include: AFP, CEA,CA19-9 PSA (males) & CA125 (females)
Infection tests include: HIV, Hepatitis B, HCV, HTLV, CMV, VDRL5
If not performed in last 12 months prior to start of study

A serum test will be done at screening and a urine test on all other days
 Complete draw if detected at Day 21

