6.2.8 Day 59 (\pm 7 days)

The following evaluations will be performed at Day 59 (\pm 7 days):

- Physical exam
- Vital signs
- Photograph and measurement of ulcer
- Clinical laboratory tests
- Infection tests
- Tumor markers
- Serum HGF

CONFIDENTIAL

- anti-HGF antibodies
- VM202 DNA levels (If DNA is detected at Day 21)
- Hemodynamic assessments (ABI, TBI, Wave Form)
- Pain VAS
- TcPO₂
- Endothelial progenitor cell assay
- Analgesic Use
- Injection site reaction assessment
- Concomitant medications
- Adverse events

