2.2 Secondary Objectives

The secondary objectives of the study will include the following exploratory evaluations:

- To investigate the effects of the intramuscular VM202 to improve pain at rest and/or to heal ischemic ulcers of the affected limb. The VAS assessment tool will be used for this evaluation:
- To evaluate the anatomic and physiological extent of collateral vessel development in subjects with critical limb ischemia as measured by MRA;
- To evaluate the change in serum HGF levels from Day 1 to Day 59;
- To evaluate the change in VM202 DNA levels from Day 1 to Day 59;
- To evaluate the immune response to HGF in subjects with CLI as measured by the change in anti-HGF antibodies from Day 1;
- To evaluate the ability of VM202 to stimulate endothelial progenitor cells as measured by the change in endothelial cell progenitor assay levels from screening to Day 59.

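### Day 59 VM202 DNA is sampled only in subjects positive at Day 21, but SAP 11 and Table 25 present it as an unlabelled dose-cohort summary

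*SAP*

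**What the plan says.** **Sampling rule.** The two documents agree. SAP 11 has "VM202 DNA levels will be collected on Day 21 and Day 59 (if DNA is detected on Day 21". The protocol's Pharmacokinetic Evaluations paragraph in section 4.1 has "levels will be measured at Days 21, and 59 (if DNA is detected at Day 21", its Day 59 visit list in 6.2.8 has "VM202 DNA levels (If DNA is detected at Day 21", and the footnote to the Day 59 DNA cell of Table 4-1 reads "Complete draw if detected at Day 21".

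**Summary rule.** SAP 11 continues: "VM202 DNA level results will be summarized using descriptive statistics at baseline and at each post baseline time point". Changes from baseline are summarised too. SAP 5 assigns PK analysis to the ITT population (at least one dose and one post-dose assessment) and defines no subset for this assay. SAP 8.3 says that only collected data are used and nothing is imputed. The Table 25 shell gives each dose cohort an ordinary Day 59 block: N, mean (SD), median, minimum and maximum, for result and for change. It carries no footnote on who was sampled.

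**Objective.** SAP 2.2 has "To evaluate the change in VM202 DNA levels from Day 1 to Day 59". Protocol 3.2 has "To evaluate the change in VM202 DNA levels from Day 1 to Day 21".

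**The concern.** Whether a subject contributes a Day 59 value depends on that subject's own earlier value of the same analyte. Subjects whose plasmid was already undetectable at Day 21 have no Day 59 sample and, with no imputation, drop out of the mean. What remains is a mean among subjects selected for persistence, printed under an ITT dose-cohort heading.

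Blood VM202 DNA is the only plasmid assay in the protocol's schedule, so this is the table a reader would use to judge how long plasmid stays in the circulation at each dose. Two misreadings are possible. A partly positive cohort can look as if it carries more plasmid at Day 59 than it does. A fully negative cohort leaves an empty cell, so the table cannot show the reassuring result that nobody was detectable.

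Separately, the SAP keeps a Day 59 change objective that this sampling rule cannot estimate for the whole cohort, while the protocol's objective stops at Day 21.

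**Working it through.** The plan states no figure on this point, so there is none to reproduce. The check asks what Table 25 would print under the stated rules.

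**Inputs from the documents.** Cohort size n = 3, or 6 if expanded after a DLT (SAP 3); four cohorts; Day 59 sample only if positive at Day 21 (SAP 11); no imputation (SAP 8.3).

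**Inputs assumed.** The documents do not give the Day 21 detection rate p, or the Day 59 level in subjects negative at Day 21. I take p from 5% to 70%. I write the negatives' Day 59 level as a fraction f of the positives' mean m, with f from 0 to 1.

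**Size in a given cohort.** With k of n positive at Day 21:

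- Table 25 prints m.
- The whole-cohort mean is [k·m + (n − k)·f·m] / n.
- The ratio is R = n / [k + (n − k)·f].

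For n = 3:

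| f | 1 of 3 positive | 2 of 3 positive |
|---|---|---|
| 0 | 3/1 = 3.0 | 3/2 = 1.5 |
| 0.25 | 3/1.5 = 2.0 | 3/2.25 = 1.33 |
| 0.5 | 3/2 = 1.5 | 3/2.5 = 1.2 |
| 1 | 1.0 | 1.0 |

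With 3 of 3 positive, R = 1 whatever f is. With 0 of 3 positive, R is undefined: Table 25 shows N = 0 and no mean. In an expanded cohort of 6 with f = 0, 1 of 6 positive gives 6/1 = 6.0 and 3 of 6 gives 6/3 = 2.0. The same ratios apply to change from baseline if pre-dose DNA is zero in everyone, which is also an assumption.

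**How often each case arises.** Assume n = 3, independent subjects, and the same p and sampling rule in all four cohorts:

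- P(empty) = (1 − p)³
- P(partly positive) = 1 − (1 − p)³ − p³
- P(at least one of four cohorts partly positive) = 1 − [1 − P(partly positive)]⁴

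| p | Empty Day 59 cell | Partly positive | At least one of four partly positive |
|---|---|---|---|
| 5% | 86% | 14% | 46% |
| 10% | 73% | 27% | 72% |
| 20% | 51% | 48% | 93% |
| 30% | 34% | 63% | 98% |
| 50% | 12.5% | 75% | 99.6% |
| 70% | 3% | 63% | 98% |

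At low detection rates the usual outcome for a cohort is a blank cell. At moderate rates it is a selected mean.

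**The case against.** **The row may be nearly empty.** The version 5.0 entry in the protocol's modification log explains the dropped PK parameters by saying that VM202 is gone from the body within hours of injection. If so, few subjects or none will be positive at Day 21, six days after the planned second dose, and there will be little to overstate. This stands. It makes the size conditional and moves the likely defect towards the blank cell. It does not supply the missing label.

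**The reduced count is visible.** Table 25 has a cohort N in the header and an N at each visit, and Listing 26 gives individual DNA levels. With three subjects per cohort a careful reader can reconstruct who was detectable. This also stands, and it means that nothing is hidden. But the N row does not say why the count fell or that it fell by selection on the outcome.

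**Counting unsampled subjects as not detected is imputation**, which SAP 8.3 rules out. This is correct, so any such count needs a written exception and must be called an assumption.

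**The rule may not cover every subject.** The log introduces the conditional draw in version 5.0, which already cites experience from the first two cohorts; the chart it replaced had an unconditional Day 59 draw. By inference, some lower-dose subjects may have been sampled at Day 59 whatever their Day 21 result. That would weaken the point for those cohorts but would put whole-cohort and positives-only means side by side in one table.

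**The stakes are limited.** The objective is an exploratory secondary one, no formal cohort comparison is planned (SAP 8.5), and DNA level is not part of the DLT definition (Protocol 7.1.9).

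**Conclusion.** The point holds as one of labelling and choice of summary. Under the stated rules the Day 59 mean and change describe Day-21-positive subjects only. They overstate the cohort level when a cohort is partly positive and its negatives are lower at Day 59: by 3.0 or 1.5 for one or two positives of three with negatives at zero, and by 1.5 or 1.2 with negatives at half the positives' mean. There is no bias if all are positive, and a blank cell if none is. The mismatch between SAP 2.2 and Protocol 3.2 stands whatever the detection rate.

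A reader might infer two stronger things that the documents do not support:

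- *That a threefold overstatement is to be expected.* That figure needs exactly one positive of three and unmeasured values set to zero. The documents give neither.
- *That this table supported the shortening of follow-up.* The reason logged for version 6.0 concerns plasmid persistence in nontarget tissues and off-target angiogenesis across preclinical and clinical studies. Nothing links it to the Day 59 blood mean, and an upward bias would work against a claim of no persistence.

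**What to change.** In SAP 11 and Table 25:

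1. Add rows for n/N subjects with detectable DNA at Day 21 and at Day 59, with subjects who have a Day 21 result as denominator.
2. Count subjects negative at Day 21 and not sampled at Day 59 as not detected at Day 59. State this as an assumption and as an explicit exception to SAP 8.3, and print the number actually sampled beside it.
3. Label the Day 59 concentrations and changes as Day-21-positive subjects sampled at Day 59. Keep those who have since cleared; restricting to Day 59 positives would select further.
4. If any subjects were sampled at Day 59 regardless of their Day 21 result under an earlier protocol version, use their measured values for n/N, and apply the same Day-21-positive restriction to concentrations in every cohort.

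In SAP 2.2, align the DNA objective with Protocol 3.2 (Day 21).

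The cost is one revised table shell and a few sentences of SAP text. No new samples or visits are needed.
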